**Table 2: Study Endpoints: Induction and Maintenance Phase Endpoints Through Week 48**

Endpoint	Name	Description	Timeframe
Primary	Eosinophil histologic response	Changes in mean number of peak eosinophils (eos) per high-power field (hpf) in gastrointestinal (GI) biopsies from baseline to Week 16	Week 16
Key Secondary	Clinical response: eosinophilic gastroenteritis (EGE) -related symptoms	
Changes from baseline in each of 5 domain scores of the Izumo Scale (APPENDIX B) from baseline
 
 
• Heartburn Symptoms domain
 
• Gastric Pain Symptoms domain
 
• Stomach Heaviness Symptoms domain
 
• Constipation Symptoms domain
 
• Diarrhea Symptoms domain
 
 
Gastric Pain Symptoms domain, Stomach Heaviness Symptoms domain, and Diarrhea Symptoms domain are Symptoms of Interest of EGE
	Weeks 16 and 48
	Clinical and histologic response composite	
The proportion of responders defined as subjects who achieve both clinical and histologic response:
 
 
• Clinical response defined as the proportion of subjects who achieve < 4/15 in each of three Symptoms of Interest (Gastric Pain Symptoms domain, Stomach Heaviness Symptoms domain, and Diarrhea Symptoms domain) scores of the Izumo Scale from baseline
 
• Histologic response defined as a > 75% reduction of peak gastric and/or duodenal eos count from baseline
 
	Weeks 16 and 48
	Safety and tolerability	Safety and tolerability evaluated by the incidence, severity and relationship to CC-93538 of adverse events (AEs), serious adverse events (SAEs), clinical laboratory abnormalities, changes in vital signs, physical examination abnormalities and the presence of anti-drug antibodies, including neutralizing antibodies when warranted	Through Week 48
Secondary	Eosinophil histologic response	Changes in mean number of peak eos per hpf in GI biopsies from baseline to Week 48	Week 48
	Eosinophil histologic response	Percent changes in mean number of peak eos per hpf in GI biopsies from baseline	Weeks 16 and 48
	Eosinophil histologic response (> 75% reduction)	The proportion of subjects achieving eosinophilic histologic response defined as a > 75% reduction of peak gastric and/or duodenal eos count from baseline, respectively	Weeks 16 and 48

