**Table 4: Table of Events for the Induction Phase**

Study Procedures	Screening a	Induction Phase Treatment Period									EGE Flare Assessment Visit e	ET Visit f	Interim 8-week Safety Follow-up Visit g	Final 16-week Safety Follow-up Visit g	
		Visit 1 b	Visit 2	Visit 3	Visit 4	Visit 5	Visit 6	Visit 7	Visit 8 c, d						
Visit Week (Window)	Day -28 to -1	Day 1	Week 1 (Day 8±3d)	Week 2 (Day 15±3d)	Week 3 (Day 22±3d) h	Week 4 (Day 29±3d) h	Week 8 (Day 57±3d) h	Week 12 (Day 85±3d) h	Week 16 (Day 113±3d) h	Week 23 (Day 162±7d)	Week 31 (Day 218±7d)				
Entry to Maintenance Phase y	-	-	-	-	-	-	-	-	X z	-	-	-	-	-	
Randomization via IWRS	-	X	-	-	-	-	-	-	-	-	-	-	-	-	
IP administration aa	-	X	X h	X h	X h	X	X	X	X	-	-	-	-	-	

Abbreviations: AE = adverse event;

COVID-19 = Coronavirus disease 2019; d

= day; ECG = electrocardiogram;

EGD = esophagogastroduodenoscopy; EGE = eosinophilic gastroenteritis; EGID

= eosinophilic gastrointestinal disorder;

ePRO = electronic patient-reported outcome;

ET = Early Termination; FCBP = female of childbearing potential;

HIV = human immunodeficiency virus;

IP = investigational product; IWRS = Interactive Web Response System;

PK = pharmacokinetic(s);

PRO = patient-reported outcome; SAE = serious adverse event;

TB = tuberculosis;

- All assessments must be completed within 4 weeks prior to Day 1, except for EGD with tissue biopsies and informed consent, which must be completed within 8 weeks prior to Day 1.
- The Day 1 assessments will serve as baseline measurements and will be conducted before dose administration.
- For subjects continuing in the Maintenance Phase, Visit 8 (Week 16) of the Induction Phase will also be the first visit in the Maintenance Phase or the Open-label Long-term Extension Phase. See [Table 5](#) and [Table 6](#) for the Table of Events for the Maintenance Phase or Open-label Long-term Extension Phase.
- In the event of scheduling challenges, EGD may be performed with a + 7 days visit window. All assessments are to be performed prior to IP administration for the first day of dosing in the Maintenance Phase.

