## 6 PROCEDURES

Assessments and procedures for the Screening Period and the Induction Phase are outlined in [Table 4](#). Assessments and procedures for the Maintenance Phase are outlined in [Table 5](#). For the Follow-up Period (Safety Follow-up Visits), assessments and procedures are included in both [Table 4](#) and [Table 5](#). Assessments and procedures for the Open-label Long-term Extension Phase are outlined in [Table 6](#). Study assessments and procedures are also described in [Section 6.1](#), [Section 6.2](#), and [Section 6.3](#). The day of administration of the first dose of IP is defined as Day 1 (pre-dose/baseline).

[figure not shown]
It is recommended that the study visits are scheduled in the morning. Whenever possible, the assessment order sequence should remain constant, and assessments should be conducted at approximately the same time of day throughout the study.

The following order for performing assessments and procedures is recommended (note that not all assessments and procedures are performed at every visit):

- EGE clinical symptom assessment instruments and PROs
- Spontaneous or solicited AE reporting
- Vital signs
- Physical examination
- Clinical laboratory tests, including blood sampling for the assessment of serum CC-93538 levels, ADA, [REDACTED]
- EGD (if applicable)
- IP administration

Throughout the study, IP administration should occur on the same day each week. For administration on study visit days, dosing should occur in the clinic. In the event a study visit can only be scheduled on a different day of the week than the usual dosing day, subjects should maintain their usual dosing schedule when possible.

The Izumo Scale will be completed weekly during the Screening, the Induction, the Maintenance and the OLE Phases, and for those subjects who are required to complete the Safety Follow-up Visits ([Section 6.3.1](#)), the Izumo Scale will be assessed at least for the prior week at each of the 2 Safety Follow-up Visits.

For the purposes of this study, adolescents are defined as subjects aged 12 to 17 years at the time of signing the ICF/assent form in Study CC-93538-EG-001 and adults are defined as subjects aged

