After completion of a training module, weekly assessments may be performed starting prior to scheduled Day 1 (baseline) for consecutive weeks during the screening period (ie, the Izumo Scale data collections during screening period are 5 times at maximum [on Day-28, Day-21, Day -14, Day -7, and Day 1]). Subjects will not be able to complete a questionnaire more than 3 days before/after it is due. Subjects are required to have completed for at least the prior 2 consecutive weeks of the Izumo Scale data collection on Day 1 (ie, for the final 2 weeks of screening preceding Day 1 that are assessed on Day -7 and Day 1) in order to be enrolled in the study.

It is expected that [REDACTED]

[REDACTED] . A telephone call

may be made to subjects as a reminder to complete [REDACTED]

[REDACTED]. Telephone calls may take place just prior to the beginning of the final [REDACTED] and [REDACTED] which serves as the study baseline.

Safety laboratory analyses and all assessments will be performed. Screening laboratory values must demonstrate subject eligibility, but may be repeated within the screening window, if necessary.

Written, signed, and dated informed consent/assent from the subject prior to the performance of any study related procedures must be obtained by the Principal Investigator or designee (refer to [Section 12.3](#) for further details regarding obtaining subjects' informed consent/assent). A copy of the signed informed consent/assent must be given to the subject for his/her records.

The following evaluations will be performed at screening as specified in the Table of Events ([Table 4](#)), after informed consent/assent has been obtained:

- Assessment of inclusion/exclusion criteria
- Demographics and baseline characteristics
- Medical history
- Prior therapy and concomitant therapy including details of the concomitant use of steroid. The use of concomitant medication and procedures will be monitored throughout the study. Refer to [Section 8](#) for prohibited concomitant therapies and permitted concomitant therapies including stable dose requirements and other restrictions.

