## **6.2 Induction Phase and Maintenance Phase**

On Day 1, prior to randomization in the Induction Phase, the baseline assessments (including laboratory assessments), as shown in [Table 4](#), will be completed. The investigator will review all available information to confirm subject eligibility.

- Screening laboratory tests will be used to determine eligibility for randomization with the exception of pregnancy tests, which will need to be confirmed by the Day 1 test results.
- A urine (or serum) pregnancy test must be performed for all FCBP on Day 1 and the results reviewed prior to randomization. A negative pregnancy test result must be obtained prior to randomization. If the urine pregnancy test result is positive but this is believed to be a false positive, the site may perform a stat serum pregnancy test at the local laboratory to confirm pregnancy status.
- Baseline laboratory tests will be performed on Day 1 for comparison with follow-up tests. However, the results of these tests will not be available prior to randomization on Day 1.
- The following instruments will be administered prior to dosing on Day 1 to serve as the baseline assessment:
  - Weekly Izumo Scale questionnaire ([Section 6.1](#) and [6.4.2.1](#)) ([APPENDIX B](#))
  - EGID Severity Score ([Section 6.4.2.2](#)) ([APPENDIX C](#) and [APPENDIX D](#))

After eligibility has been confirmed and baseline assessments have been completed, eligible subjects will be randomized to treatment on Day 1. The first 3 weekly SC doses will be administered in the clinic. Subjects will remain in the clinic for at least 30 minutes following dosing for observation. Subsequent visits, assessments and procedures will be performed as per the Table of Events ([Table 4](#) for the Induction Phase and [Table 5](#) for the Maintenance Phase). For subjects weighing  $\geq 30$  kg and  $<40$  kg, the first 3 weekly SC doses will be administered in the clinic with confirmation of concomitant medications and AEs, and those subjects will remain in the clinic for at least 1 hour following dosing for observation and be monitored every two weeks by the site staff by telephone (but not limited to telephone) between regularly scheduled visits until Week 16 (ie, Week 6 [Day  $43 \pm 3$  days], Week 10 [Day  $71 \pm 3$  days], and Week 14 [Day  $99 \pm 3$  days]).

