Subjects will complete the Izumo Scale questionnaire weekly during the Screening Period via a handheld device for at least the 2 consecutive weeks before the IP administration on Day 1 (ie, for the final 2 weeks of screening preceding Day 1 that are assessed on Day -7 and Day 1). Every effort should be made to enhance subject adherence to the Izumo Scale Questionnaire completion and limit the amount of missing data, which is critical to ensure interpretability of the Izumo Scale assessment in this study. For example, ePRO instrument's reminder alarms will allow subjects to select the timing for their alarm within a standardized window (at the same time as much as possible) of weekly completion of questionnaire, and ongoing surveillance of weekly completion data will also occur in order to correct any issues as close to real time as possible.

Subjects will not be able to complete a questionnaire more than 3 days before/after it is due and will not be able to go back and make any corrections or changes to the data originally entered. This information will be automatically captured and maintained in the ePRO system of the electronic data capture system (EDC).

The Izumo Scale Questionnaire will be administered at the same time weekly as much as possible via an ePRO instruments from Day 1 through Week 48 (through the duration of the Induction and Maintenance Phases) of the study, through the ET Visit (if applicable), and first year of the OLE Phase and at least for the prior week period (7 days) preceding each of the 2 Safety Follow-up Visits (if applicable) according to the Table of Events ([Table 4](#), [Table 5](#), and [Table 6](#)).

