### **9.6.3 Analysis of Secondary Efficacy Endpoints**

#### **9.6.3.1 Analyses Methods**

##### Continuous variables:

- Changes in mean number of peak eos count per hpf from baseline to Week 48
- Changes from baseline in each of 5 domain scores of the Izumo Scale (Weeks 14, 16, 32, and 48)
- Changes from baseline in total score of EGID Severity Score (Weeks 16, 32, and 48)
- Percent changes in mean number of peak eos per hpf in GI biopsies from baseline (Weeks 16 and 48)
- The time until concomitant corticosteroid treatment to zero (and continued by Week 48) (from Week 16 through Week 48)

The analysis for continuous variables of the secondary endpoints will be conducted on the ITT population using the ANCOVA model with treatment group (CC-93538 360 mg SC once weekly, CC-93538 360 mg SC once every other week, and placebo), prior steroid use (yes or no), and baseline values included in the model. Point estimates for the mean difference between the treatment groups using the LS mean changes and corresponding 95% Wald CI will be reported. The transition from the Maintenance Phase to the OLE Phase will be treated as ICE. Missing data and ICEs will be handled via the same strategy as for the primary analysis.

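### The continuous Izumo change runs from the Day 1 score to single listed weeks with no averaging rule; mean scores over short windows would make this key secondary estimate more precise

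*Combined protocol and SAP*

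**What the plan says.** **Collection.** Section 6 states: "The Izumo Scale will be completed weekly during the Screening, the Induction, the Maintenance and the OLE Phases". For enrolment, Section 6.1 adds: "Subjects are required to have completed for at least the prior 2 consecutive weeks of the Izumo Scale data collection on Day 1". These are the Day -7 and Day 1 scores, and up to five screening scores are possible.

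**Baseline.** A Table 4 footnote states: "The Day 1 assessments will serve as baseline measurements and will be conducted before dose administration". Section 6.2 introduces a list that includes the weekly Izumo questionnaire with: "The following instruments will be administered prior to dosing on Day 1 to serve as the baseline assessment". Section 6.1, however, explains the ban on endoscopy in the last 2 weeks of screening by saying that the electronic patient-reported outcomes are then being evaluated for the baseline time point.

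**Outcome weeks.** Table 2 gives the key secondary change in the five domain scores the timeframe "Weeks 16 and 48". Section 9.6.3.1 gives "Changes from baseline in each of 5 domain scores of the Izumo Scale (Weeks 14, 16, 32, and 48" and analyses change by ANCOVA with the baseline value as a covariate. No passage averages the continuous score over weeks or specifies a repeated-measures model.

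**Same scale, responder endpoint.** For the proportion below 4/15 in all three symptoms of interest, Section 9.6.3.1 uses Weeks 14 to 16, 30 to 32 and 46 to 48. It does not say how the weekly scores in a window combine. Table 2 lists this endpoint at Weeks 16 and 48.

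**Status.** Only the primary endpoint is formally tested (Section 9.6.3.1, Multiplicity Adjustment). Izumo comparisons carry nominal p-values.

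**The concern.** The Izumo change is the first-listed key secondary endpoint and the main patient-reported evidence in a trial sized on eosinophil counts alone. About 30 v 15 subjects contribute at Week 16. At Week 48, after 1:1 re-randomisation of the active group, there are at most about 15 per arm. A single weekly score on a 0-15 domain carries week-to-week variation that a short mean would reduce. The adjacent scores are already collected, so a single-week analysis leaves usable information out of a small comparison.

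The text is also inconsistent. Table 2, the two lists in Section 9.6.3.1, Section 6.1 and Section 6.2 do not give one definition of the baseline and follow-up value on this scale.

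**Working it through.** **The plan's own figure.** No sample size, power, SD or correlation is stated for Izumo. The stated sample size, for the primary endpoint, reproduces. With a two-sample t-test, two-sided 0.05, difference/SD = 70/70 = 1 and 2:1 allocation, power is 78.5% at 24 + 12 and 81.8% at 26 + 13, so 39 is the smallest 2:1 total reaching 80%. Then 39/0.9 = 43.3, which is 44, or 45 at 2:1. Nothing here disputes that figure.

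**Formula.** Take the single-week score variance as 1, equal at baseline and follow-up. Let *rw* be the average correlation between weeks in one window and *rb* the baseline-to-follow-up correlation. With *p* baseline and *r* follow-up scores averaged, the ANCOVA residual variance is

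V(p,r) = [1 + (r-1)·rw]/r - p·rb²/[1 + (p-1)·rw].

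The single-to-single case is V(1,1) = 1 - rb².

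**Assumed ranges:** rw 0.5 to 0.9 and rb 0.2 to 0.6, with rb ≤ rw.

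**Central case, rw = 0.7, rb = 0.4:**
- Single to single: 1 - 0.16 = 0.840.
- Two baseline scores, one follow-up: 1 - 0.32/1.7 = 0.812. SE ratio √(0.812/0.840) = 0.983.
- One baseline score, three follow-up: 2.4/3 - 0.16 = 0.640. SE ratio 0.873.
- Two baseline, three follow-up: 0.800 - 0.188 = 0.612. SE ratio 0.853; effective sample size × 0.840/0.612 = 1.37.

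**SE ratios against single-to-single, central case and the cases that set the limits:**

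| rw | rb | baseline mean only | follow-up mean only | both | effective N |
|---|---|---|---|---|---|
| 0.9 | 0.2 | 0.999 | 0.965 | 0.964 | ×1.08 |
| 0.7 | 0.4 | 0.983 | 0.873 | 0.853 | ×1.37 |
| 0.5 | 0.5 | 0.943 | 0.745 | 0.667 | ×2.25 |
| 0.6 | 0.6 | 0.927 | 0.764 | 0.665 | ×2.26 |

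The SE falls by about 4% to 33% with both means, by 3.5% to 25.5% with the follow-up mean alone and by 0.1% to 7% with the baseline mean alone. The baseline part is small because ANCOVA already adjusts for baseline.

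**In terms of detectable difference.** The difference with 80% power, in single-week SDs for the central case (two-sample t calculation on the residual SD), falls from 0.83 to 0.71 at 30 v 15 and from 0.97 to 0.83 at 15 v 15. A difference with 80% power under single-to-single at 30 v 15 would have 84% (rw 0.9, rb 0.5), 91% (0.7, 0.4) or 95% (0.5, 0.3).

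**The case against.** **Single-week follow-up is an inference.** No sentence says that the Week 16 or Week 48 value is one weekly score. The listed Week 14 has no matching Week 30 or 46 and is not a scheduled site visit in Table 4, so the list may have been meant as the responder window. Section 9.1 leaves unexplained detail to a SAP, and the file reviewed contains no separate SAP text. This stands. It limits the claim to what the protocol text shows, and it strengthens the case for stating one definition.

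**Missing entries.** A reader might infer that a missed Week 16 entry forces avoidable imputation because the Week 15 score goes unused. The documents do not support that. Missing values are multiply imputed under missing at random, the imputation model is not described, and it may use earlier weekly scores. Section 6.4.2.1 also provides reminders, ongoing surveillance of completion and a 3-day entry margin on either side.

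**The two baseline scores.** A reader might think the unused Day -7 score is the main loss. It is not; its share is about 2% of the SE in the central case.

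**Assumptions.** The gain depends on correlations that the documents do not give. Equal variances are only approximate, because entry requires at least 4/15 in one of the three symptom domains. The direction nevertheless holds under this model whenever weeks in a window correlate below 1.

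**Estimand.** A score at Week 16 is a legitimate target, and a windowed mean is a different one. This is a real trade-off, though small: corticosteroids are to stay stable until Week 16, and dosing runs through Weeks 15 and 47, so both windows describe on-treatment status at the end of a phase.

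**Conclusion.** The point holds as a precision improvement and a request for consistency. As written, the Izumo baseline is the Day 1 score, and the continuous change is listed at separate weeks without averaging, while weekly scores exist and the responder endpoint on the same scale has three-week windows. If single weeks are indeed used, windowed means would lower the SE by about 4% to 33%, and by about 15% at rw 0.7 and rb 0.4, mostly from the follow-up side. These sizes rest wholly on assumed correlations and equal variances.

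The issue does not bias the comparison, change the type I error or touch the primary analysis. It concerns one key secondary estimate with nominal p-values. A reader might conclude that the plan definitely discards the neighbouring scores, but the text leaves that open.

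**What to change.** In Section 9.6.3.1, and to match in Section 6.2, the Table 4 baseline footnote and Table 2:

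1. Define the Izumo baseline, for both the change and the covariate, as the mean of the Day -7 and Day 1 domain scores.
2. Define the Week 16 and Week 48 values as the mean of the available weekly scores in Weeks 14-16 and 46-48, the windows already given for the responder endpoint, using whatever scores in the window are present. If Week 32 stays listed, use Weeks 30-32 in the same way.
3. Say whether Week 14 is a separate time point or the start of a window, and how weekly scores combine for the responder endpoint.
4. State whether weekly scores outside the window enter the imputation model.
5. Keep the change from Day 1 to the single week as a supportive analysis.
6. Align the baseline wording in Section 6.1 with the definition chosen.

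**Cost.** No new data and no extra subject burden, but protocol wording changes as well as SAP text and programming, and this should be settled before database lock. The estimate then describes the last few weeks of the phase instead of one week. If a SAP already defines these windows, only the protocol sections need aligning.

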**Table 2: Study Endpoints: Induction and Maintenance Phase Endpoints Through Week 48**

Endpoint	Name	Description	Timeframe
Secondary (continued)	Clinical responder definition	Proportion of subjects who achieve < 4/15 in each of three Symptoms of Interest scores using the Izumo Scale from baseline  Gastric Pain Symptoms domain, Stomach Heaviness Symptoms domain, and Diarrhea Symptoms domain are Symptoms of Interest of EGE	Weeks 16 and 48
	Clinical response: Eosinophilic gastrointestinal disorder (EGID) Severity Score	Changes in total score of EGID Severity Score consisting of 8 symptom/laboratory scores and 2 medical history related questions using EGID Severity Score ( APPENDIX C for subjects ≥ 20 years at the time of signing the informed consent form [ICF]) or consisting of 8 symptom/laboratory scores and 3 general condition related questions ( APPENDIX D for subjects from 12 to 19 years at the time of signing the ICF/assent) from baseline	Weeks 16 and 48
	Time to event	The time to event of EGE flare	Through Week 48
	Time to event	The time to event of use of rescue therapy	Through Week 48
	Time to event (subjects who use concomitant treatment only)	The time until concomitant corticosteroid use to zero (and continued by Week 48)	From Week 16 through Week 48
	Proportion of subjects with event (subjects who use concomitant treatment only)	The proportion of subjects for whom the dose of concomitant steroids is reduced to zero	Weeks 24, 32, 40, and 48
	Pharmacokinetics (PK)	Trough concentrations of CC-93538 through Week 48	Through Week 48

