#### Intent-to-treat (ITT) Population

The ITT population will consist of all randomized subjects regardless of whether or not the subject received IP (CC-93538 or placebo).

The ITT population will be used as the primary population for all efficacy parameters. Subjects who prematurely withdraw from the trial for any reason and for whom an assessment is not performed for any reason will still be included in the ITT analyses. Subjects who received incorrect IP from what was randomized will be included in the treatment group according to the intended randomization. Subjects who were randomized with a misreported stratum will be analyzed according to their original (misreported) stratum.

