##### Dichotomous variables:

- The proportion of responders defined as subjects who achieve both clinical and histologic response (Weeks 16 and 48):
  - Clinical response is defined as the proportion of subjects achieve  $< 4/15$  in all Symptoms of Interest (Gastric Pain Symptoms domain, Stomach Heaviness Symptoms domain, and Diarrhea Symptoms domain) of the Izumo Scale
  - Histologic response is defined as a  $> 75\%$  reduction of peak gastric and/or duodenal eos count from baseline

- The proportion of subjects achieving eosinophilic histologic response defined as a > 75% reduction of peak gastric and/or duodenal eos count from baseline (Weeks 16 and 48)
- The proportion of subjects who achieve < 4/15 in all Symptoms of Interest (Gastric Pain Symptoms domain, Stomach Heaviness Symptoms domain, and Diarrhea Symptoms domain) of the Izumo Scale (Weeks 14 to 16, 30 to 32, and 46 to 48)
- The proportion of subjects for whom the dose of concomitant steroids is reduced to zero (Weeks 24, 32, 40, and 48)

The analysis of the response endpoint will be conducted on the ITT population using the Cochran-Mantel-Haenszel (CMH) test stratified by concomitant corticosteroid treatment at baseline (yes or no). In case the Mantel-Fleiss criterion is not met, the Fisher's exact test will be performed instead of the CMH test. For treatment comparison between a CC-93538 dose and placebo, the 2-sided 95% stratified Newcombe CI ([Yan, 2010](#)) for the difference in proportions using the CMH weights will be provided. Missing data and any observed data after rescue therapy/prohibited medication which may impact the efficacy assessment will be set as non-responders.

Time to event data:

- The time to event of EGE flare (Through Week 48)
- The time to event of use of rescue therapy (Through Week 48)
- The time until concomitant corticosteroid use to zero (From Week 16 through Week 48)

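### Section 9.6.3.1 contradicts Table 2 on the corticosteroid endpoints: time to zero dose is also put under ANCOVA, the sustained condition is dropped from the log-rank version, and ITT is named where Table 2 says users only

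*Combined protocol and SAP*

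**What the plan says.** Table 2 has two corticosteroid endpoints, both secondary and both limited to "subjects who use concomitant treatment only". One is typed as time to event: "The time until concomitant corticosteroid use to zero (and continued by Week 48"). The other is the proportion whose dose is reduced to zero at Weeks 24, 32, 40 and 48.

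Section 9.6.3.1 handles them as follows:

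- **Continuous variables.** It lists "The time until concomitant corticosteroid treatment to zero (and continued by Week 48) (from Week 16 through Week 48"). The method is: "The analysis for continuous variables of the secondary endpoints will be conducted on the ITT population using the ANCOVA model", with baseline values as a covariate and results given as least-squares mean changes.
- **Time to event data.** It lists the same endpoint again, as "The time until concomitant corticosteroid use to zero (From Week 16 through Week 48"). The methods are Kaplan-Meier percentiles of the time to the first event and a stratified log-rank test. No population is named here.
- **Dichotomous variables.** For the proportion at zero: "The analysis of the response endpoint will be conducted on the ITT population using the Cochran-Mantel-Haenszel (CMH) test". The two strata are users and non-users of corticosteroid at baseline. Fisher's exact test replaces it if the Mantel-Fleiss criterion fails.

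The general rule in Section 9.2 is: "The ITT population will be used as the primary population for all efficacy parameters". Section 6.2 admits subjects who need no concomitant treatment. Sections 3.1.3 and 6.2 let the corticosteroid dose rise again, up to the baseline dose, if symptoms worsen after tapering.

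**The concern.** Three rules for the same endpoints conflict.

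1. **Method.** ANCOVA needs an observed value for each subject and, as specified here, a baseline value. A stopping time has no baseline value and no change from baseline, and a subject who never stops has no observed time.
2. **Event.** The dose may be raised again after a taper, so first zero and sustained zero can differ. A subject who reaches zero and restarts is not an event under Table 2, but can be counted as one under the time-to-event bullet, which drops the sustained condition and is followed by first-event wording.
3. **Population.** Non-users are in the trial, so ITT and users are different sets. No rule says whether a subject with no steroid to stop counts as zero, as not reduced, or not at all.

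Reducing concomitant corticosteroid use is a stated secondary objective. As written, one endpoint can give two analyses, two event counts and several denominators, and the choice could be made after unblinding.

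**Working it through.** The plan gives no figure for these endpoints, so there is none to reproduce. The comparison of the sections is the main check:

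| | Table 2 | 9.6.3.1 continuous | 9.6.3.1 time to event | 9.6.3.1 dichotomous |
|---|---|---|---|---|
| Time to zero: type | time to event | ANCOVA | KM, log-rank | – |
| Time to zero: held to Week 48 | yes | yes | not stated | – |
| Population | users only | ITT | not named; ITT through 9.2 | ITT (proportion at zero) |

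The calculations below are illustrations. **From the documents:** 45 subjects randomised 2:1, with the active arm re-randomised 1:1, which gives 15 per maintenance arm before dropout; Weeks 16 to 48 is 32 weeks; the taper is 2.5 mg/week from at most 10 mg/day, so 10/2.5 = 4 weeks from the highest dose. **Assumed:** user share, stopping and restart rates, and stop times uniform from 4 to 20 weeks after Week 16 (mean 12).

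**Population, proportion at zero.** With equal arms the CMH weights are proportional to stratum size. If all non-users are coded alike, their stratum difference is 0, so the ITT difference is the user difference × users/15. For a user difference of 0.40:

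- 12 users per arm: 0.40 × 12/15 = 0.32
- 10 users: 0.27
- 8 users: 0.21
- 5 users: 0.13

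With 10 users per arm and 7 v 3 at zero:

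| Set | Active | Placebo | CMH p | Fisher p |
|---|---|---|---|---|
| Users | 7/10 = 70% | 3/10 = 30% | 0.081 | 0.179 |
| ITT, non-users not reduced | 7/15 = 47% | 3/15 = 20% | 0.081 | 0.245 |
| ITT, non-users at zero | 12/15 = 80% | 8/15 = 53% | 0.081 | 0.245 |

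The CMH statistic is (7 − 5)²/1.316 = 3.04 in every row, because a stratum with identical outcomes adds nothing. Under the usual rule that the Mantel-Fleiss quantity must exceed 5 (an assumption; the documents give no threshold), this example would fall back to Fisher.

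**Population, KM median, 70% of active users stopping.**

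- Users: 0.7(x − 4)/16 = 0.5, so x = 15.4 weeks.
- ITT, 10 of 15 users, non-users as non-events: the curve peaks at 0.7 × 10/15 = 0.467, so the median is not reached.
- ITT, non-users as events at time 0: 0.333 + 0.467(x − 4)/16 = 0.5, so x = 9.7 weeks.

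**Event definition.** Assume 10 users per arm, 80% v 60% ever reaching zero and 70% v 30% staying there. The difference is 0.20 on first zero and 0.40 on sustained zero. In 6,000 simulated trials per definition, with non-events censored at 32 weeks, log-rank p < 0.05 occurred in 15% and 43%. With no restarts the definitions agree. More restarts on active would reverse the direction.

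**ANCOVA.** Assume 70% v 30% stop, with the same timing among stoppers.

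- Never-stoppers set to 32 weeks: active 0.7 × 12 + 0.3 × 32 = 18.0; placebo 0.3 × 12 + 0.7 × 32 = 26.0; difference −8.0 weeks.
- Never-stoppers treated as missing at random, the primary missing-data strategy that this paragraph invokes: 12 − 12 = 0.0 weeks.

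The protocol does not say which applies.

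**The case against.** The strongest reply is that the intent can be recovered. Section 2 says the endpoints are described in the tables, so the bullets in 9.6.3.1 may be short labels. The first-event wording is shared with flare and rescue and could refer to a sustained-zero event. Users only can be read together with ITT as randomised users analysed as randomised, and a non-user has no dose to reduce. The amendment history shows the time-to-event method being added later, so the ANCOVA bullet looks like a leftover. Section 9.1 sends further detail to a separate SAP.

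Part of this stands. The intended analysis is probably Table 2's, and coding non-users as events at time 0 is a strained reading. A subject followed to Week 48 on steroid is observed rather than missing, so the 0.0-week ANCOVA result is only one possible reading. For Kaplan-Meier and log-rank, ITT comes only from the general rule in Section 9.2. The illustrative sizes rest on assumed rates, ignore the planned dropout of about 10% by Week 16, and let no one stop before 4 weeks although lower starting doses could taper sooner.

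It does not remove the conflict. No section says Table 2 prevails, and Section 9.2 points the other way. Section 9.1 defers details the protocol leaves unexplained, whereas here the protocol explains the same endpoint in incompatible ways. A recoverable intent makes the correction easy but does not make the text right.

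**Conclusion.** The concern holds and should be fixed. The ANCOVA entry is wrong if followed. The missing sustained condition and the ITT wording leave the event and the denominator open for a stated secondary objective.

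The size depends on inputs the documents do not give: user share, stopping rates and restart rates. Under the assumptions shown, the reported active-arm percentage can lie anywhere from 47% to 80% through coding alone, and the risk difference shrinks in proportion to the user share. The stratified CMH p-value does not change if all non-users are coded alike; the Fisher fallback does. Section 9.6.3.1 makes every p-value other than the primary one nominal, so formal inference on the primary endpoint is unaffected. The damage is to the estimates and how they would be read.

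**What to change.** In Section 9.6.3.1, with the SAP aligned:

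1. Delete the time-to-zero bullet from the continuous list and keep Kaplan-Meier and log-rank for that endpoint.
2. In the time-to-event bullet, use Table 2's event: zero dose, continued to Week 48.
3. State that both corticosteroid endpoints are analysed in ITT subjects on concomitant corticosteroid at baseline. This reads Table 2's restriction as use at baseline, which is the randomisation stratum. That stratum is then constant, so CMH, the Newcombe interval and log-rank reduce to their unstratified forms. The Fisher fallback can stay.

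While editing, confirm that the SAP, which is not in the text reviewed, says how never-stoppers, entry to the open-label extension, rescue therapy and dropout (including dropout at zero dose before Week 48) enter the time-to-event analysis, preferably in line with the non-responder rule already set for the dichotomous endpoints.

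The cost is a few lines of protocol and SAP wording. There is one analysis fewer, no new data, and no change to treatment or visits.
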